10.1.4 Missing Data Imputations

Missing data will be imputed using the following methods for the efficacy analyses:

- Non-Responder Imputation (NRI): the NRI analysis will categorize any subject who has a missing value at a specific visit as a non-responder for that visit. The only exception is when the subject is a responder both before and after this specific visit window, within the same analysis period, then the subject will be categorized as a responder for the visit. The NRI will be the primary approach in the analyses of categorical variables.
- Last Observation Carried Forward (LOCF): The LOCF analyses will use the completed evaluation from the previous visit within the particular analysis period for efficacy measures assessed to impute missing data at later visits in the same analysis period. Baseline efficacy evaluations will not be carried forward. Of note, post-baseline observations from Part A can be carried

forward to the ITT_B_RZB subjects since treatment is the same. LOCF will be the primary approach in the analyses of continuous variables, and the secondary approach in the analyses of categorical variables.

- As-Observed Cases (OC): The as-observed analysis will not impute values for missing evaluations, and thus a subject who does not have an evaluation on a scheduled visit will be excluded from the as-observed analysis for that visit. As-observed analysis will be the secondary approach in the analysis of continuous variables.
- Multiple Imputation (MI): The MI analysis will be used as sensitivity approach to impute missing data in primary and ranked secondary endpoints. The variables to be included in the imputation model are listed below. If MI is not applicable due to the nature of our data (e.g., MCMC algorithm does not converge), logistic regression or mixed effect model repeat measurement (MMRM) methods will be applied as sensitivity approach, whichever applicable.

The Multiple Imputation analysis will be carried out in three steps.

- Imputation of missing data. The imputation will be generated for each efficacy endpoint measurement. The variables to be included in the imputation model are: Baseline disease severity (PASI and sPGA), Baseline weight, treatment group, prior TNF exposure, and measurements at each visit from randomization (or re-randomization) up to the end of the analysis period. For each endpoint, 20 'complete' datasets will be generated using SAS PROC MI. The imputed post-baseline measurements will be rounded to the same precision as the observed data before the determination of responder status (e.g., PASI 90).
- Analysis of imputed data sets. A CMH test, stratified by stratification factors, will be used to analyze categorical endpoints in each imputed dataset.
- Synthesis of imputation and analysis results. SAS PROC MIANALYZE will be used to generate the final inferences of the risk difference between treatment groups.

Of note, subjects who discontinued due to AE – "Worsening of disease under study" will be counted as non-responders in all visits thereafter in the NRI and MI analyses, and will have their last observation prior to discontinuation carried forward in the LOCF analyses.

10.2 Primary Efficacy Analysis

Primary Efficacy Analysis in Part A:

There are co-primary endpoints to assess the efficacy of risankizumab for the treatment of moderate to severe plaque psoriasis. These are as follows:

- Achievement of $\geq 90\%$ reduction from baseline PASI score (PASI 90) at Week 16
- Achievement of an sPGA of clear or almost clear (0 or 1) at Week 16

The primary null hypotheses are that risankizumab is not different from adalimumab in achieving $\geq 90\%$ reduction from baseline in the Psoriasis Area and Severity Index score (PASI 90) and sPGA of clear (0) or almost clear (1) at Week 16.

The achievement of PASI 90 at Week 16 is the first co-primary endpoint and is a binary variable with values of 0 or 1. The difference in proportion responding between treatment arms will be estimated and tested using the Cochran-Mantel-Haenszel risk difference estimate stratified by the randomization factors of baseline weight (≤ 100 kg versus > 100 kg) and prior exposure to TNF antagonists (0 versus ≥ 1).

The achievement of a sPGA of clear or almost clear at Week 16 is the second co primary endpoint and is a binary variable with values of 0 or 1. The analysis of the sPGA co-primary endpoint will be identical to that of the PASI 90 co-primary endpoint detailed above.

The co-primary endpoints of PASI 90 and sPGA clear or almost clear need to be significant simultaneously. Both endpoints compared to ADA will be tested using a two-sided test with a type I error of 0.05.

The primary analysis will be carried out in the ITT_A Population and the PP_A Population. Non-responder imputation will be used as the primary approach for missing values. LOCF and MI will be performed as sensitivity analyses.

Primary Efficacy Analysis in Part B:

The primary endpoint in Part B is the achievement of PASI 90 at Week 44 for those subjects who are re-randomized at Week 16. This endpoint will be tested independently with a type I error rate of 0.05, for the ITT_B_RR Population. A sensitivity analysis will also be performed on the same endpoint for the PP_B_RR Population.

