4.1.2 Method of assigning patients to treatment groups

Through the utilization of Interactive Response Technology/Tool (IRT), patients will be initially randomized to receive BI 655066 or adalimumab in a ratio of 1:1.

After the eligibility criteria are confirmed, the patient will be randomized 1:1 to either BI 655066 or adalimumab on Day 1 (Visit 2) through IRT call or website entry. At visits where study medication is to be administered or dispensed to the patient, study sites will be required to complete the medication resupply module in the IRT.

Patients initially randomized to adalimumab and with a PASI response of \geq PASI 50 and $<$ PASI 90 at Week 16 will be re-randomised 1:1 to receive either BI 655066 or adalimumab (refer to [Section 3.1](#)). Patients initially randomized to BI 655066 will stay on BI 655066. Patients initially randomized to adalimumab and \geq PASI 90 at Week 16 will continue on adalimumab. Allocation of patients to the three treatments (who continue on BI 655066 / who will be switched from adalimumab to BI 655066 / who will continue on adalimumab) from Week 16 onwards through EOT will be realized by the IRT. The study personnel will enter the PASI score into the IRT system at Visit 2 and at Visit 8 (Week 16).

Details regarding the use of the IRT are described in the site-user manual available in the ISF.

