7.3.2 Secondary endpoint analyses

Key secondary endpoints:

The achievement of PASI 75 at Week 16 is a binary variable with values of 0 or 1. The analysis of this endpoint will be identical to that of the PASI 90 co-primary endpoint detailed in the [Section 7.3.1](#).

The achievement of PASI 100 at Week 16 is a binary variable with values of 0 or 1. The analysis of this endpoint will be identical to that of the PASI 90 co-primary endpoint detailed in the [Section 7.3.1](#).

The achievement of PASI 90 at Week 44 is a binary variable with values of 0 or 1. The analysis of this endpoint will be identical to that of the PASI 90 co-primary endpoint detailed in the [Section 7.3.1](#). Note that this endpoint will only be analysed for patients who are re-randomized at Week 16 (i.e., only for Arm A and Arm B defined in [Section 7.2](#)).

Other secondary endpoints:

Other secondary endpoints will be summarized descriptively.

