7.6 RANDOMISATION

At Visit 2, patients will be randomized in blocks to double-blind treatments, stratified by weight (≤ 100 kg vs. >100 kg) and prior exposure to TNF antagonists (0 vs. ≥ 1). Patients will be randomized to BI 655066 or adalimumab in a ratio of 1:1 within each level of stratification.

Patients originally randomized to BI 655066 150mg will stay on BI 655066 150mg. Patients who are originally randomized to adalimumab will be separated into three groups at Week 16 depending on their Week 16 PASI score. Patients will be switched to BI 655066 if they don't achieve PASI 50 at Week 16. Patients will continue on adalimumab if they achieve PASI 90 at Week 16. Patients will be re-randomized in a 1:1 ratio to either BI 655066 or adalimumab in a second double-blinded portion of the trial if they achieve PASI 50 but not PASI 90 at Week 16.

BI will arrange for the randomization and the packaging and labelling of trial medication. The randomization lists will be generated using a validated system, which involves a pseudo-random number generator so that the resulting treatment will be both reproducible and non-predictable. The block sizes will be documented in the CTR. Access to the codes will be controlled and documented.

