At Week 16, subjects initially on adalimumab and \geq PASI 90 will be stay on adalimumab. These subjects will receive 2 syringes of risankizumab placebo at Week 16, 20, 28 and 32. They will also receive 1 syringe of adalimumab at Weeks 17, 19, 21, 23, etc. up to Week 41.

At Week 16, subjects initially on adalimumab and \geq PASI 50 and $<$ PASI 90 will be re-randomized at a 1:1 ratio to risankizumab or adalimumab. Subjects re-randomized to risankizumab will receive 2 syringes of risankizumab (2×75 mg) at Week 16, 20 and 32, and 2 syringes of risankizumab placebo at Week 28. They will also receive 1 syringe of adalimumab placebo at Weeks 17, 19, 21, 23, etc. up to Week 41. Subjects re-randomized to adalimumab will receive 2 syringes of risankizumab placebo at Week 16, 20, 28 and 32. They will also receive 1 syringe of adalimumab at Weeks 17, 19, 21, 23, etc. up to Week 41.

Figure 1. Trial Design

BI 655066 is risankizumab.

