4.3 Sample Size

This study is designed to show a benefit of risankizumab over adalimumab in terms of PASI 90 response and static Physician Global Assessment (sPGA) of clear or almost clear (sPGA of 0 or 1) at Week 16. This study is also powered to show a benefit in PASI 90 response at Week 44 between the subjects re-randomized to continue on adalimumab vs. subjects randomized to risankizumab at Week 16.

Based on the assumption that the Week 44 PASI 90 rate will be approximate 40% for adalimumab and 70% for risankizumab for the subjects who are re-randomized at Week 16, a total of 120 subjects will result in > 90% power for the primary efficacy analysis in Part B using a type-I error rate at 5%. See Table 1 sample size calculations for different scenarios. Assuming for those subjects originally randomized to adalimumab the response rate at Week 16 for PASI 90 and PASI 50 are 45% and 85%, respectively, then this leaves approximately 40% of subjects expected to fall in the more than or equal

to PASI 50 and less than PASI 90 range and thus be eligible for re-randomization. This requires that 300 (40% of 300 = 120) subjects be randomized to adalimumab at randomization.

Based on the outcome from Trials 1311.1 and 1311.2, the PASI 90 response rate at Week 16 is assumed to be at least 65% in the risankizumab arm. For the primary analysis comparing risankizumab to adalimumab, sample sizes of 300 per arm will allow for > 90% power assuming 70% and 50% PASI 90 response rates for risankizumab and adalimumab, respectively. See [Table 2](#) for more sample size calculations.

Table 1. Sample Sizes for 90% Power for Testing Against Adalimumab Using PASI 90 at Re-Randomization

Risankizumab	Adalimumab	Delta	Re-Randomization Ratio Risankizumab:Adalimumab = Total N
65%	40%	25%	82:82 = 164
70%	45%	25%	80:80 = 160
70%	40%	30%	56:56 = 112
75%	45%	30%	54:54 = 108
80%	50%	30%	51:51 = 102

Table 2. Sample Sizes for 90% Power for Testing Against Adalimumab Using PASI 90

Risankizumab	Adalimumab	Delta	Randomization Ratio Risankizumab:Adalimumab = Total N
65%	50%	15%	226:226 = 452
70%	55%	15%	217:217 = 434
70%	50%	20%	124:124 = 248
75%	55%	20%	118:118 = 236
70%	45%	25%	80:80 = 160
75%	50%	25%	77:77 = 154

Based on the outcome from Trials 1311.1 and 1311.2, the achievement of sPGA clear or almost clear rate at Week 16 is assumed to be at least 85% in the risankizumab arm.

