10.0 Efficacy Analysis

10.1 General Considerations

The treatment effect will be evaluated based on a two-sided significance level of 0.05 (when rounded to three decimal places).

Efficacy variables will be summarized in all ITT populations. The efficacy analysis will be conducted in the ITT_A and the ITT_B_RR populations. Only the primary and ranked secondary variables will be analyzed for the per-protocol populations using primary approach to handle missing data as described below.

Subjects' actual weight category and prior TNF antagonist exposure will be used as the strata in the stratified analyses.

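### The Part B Week 44 test does not use Week 16 PASI improvement, which is known before re-randomisation; adjusting for it would be a cheap but modest gain in precision

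*SAP*

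**What the plan says.** Patients who start on adalimumab enter the Part B comparison "if they achieve PASI 50 but not PASI 90 at Week 16" (Protocol 7.6). They are then "re-randomized at a 1:1 ratio to risankizumab or adalimumab" (SAP 4.2). Both scores needed to compute the improvement are on record before that step. Protocol 4.1.2: "The study personnel will enter the PASI score into the IRT system at Visit 2 and at Visit 8 (Week 16".

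SAP 5.2 stratifies the re-randomisation by weight and prior TNF exposure. SAP 10.1 names the same two factors as the strata for all stratified analyses, and SAP 10.1.1 gives the Mantel-Haenszel risk difference. For PASI 90 at Week 44, SAP 10.2 adds: "This endpoint will be tested independently with a type I error rate of 0.05, for the ITT_B_RR Population". Protocol 7.3.2 gives this endpoint the same analysis as the Week 16 PASI 90 co-primary endpoint and limits the population: "Note that this endpoint will only be analysed for patients who are re-randomized at Week 16".

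On size, SAP 4.3 assumes Week 44 rates of "approximate 40% for adalimumab and 70% for risankizumab" and says that "a total of 120 subjects will result in > 90% power". Its Table 1 gives 56 per arm as the minimum for 90% power at those rates.

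Week 16 improvement is not a stratum, a covariate or a subgroup factor for this endpoint; SAP 10.5 lists PASI at baseline only. It could enter indirectly through the multiple-imputation model in SAP 10.1.4, but each imputed data set is still tested on the two stratification factors.

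**The concern.** Re-randomised patients range from just past PASI 50 to just short of PASI 90. Their starting distance from the Week 44 target therefore varies widely, and it is measured before the second allocation. If that distance predicts Week 44 PASI 90, a test that ignores it carries avoidable variance. In any one trial, a chance difference between arms in Week 16 response also moves the estimate without correction.

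This matters more in Part B than in Part A. Part B plans 120 patients against a Table 1 minimum of 112, with no stated allowance for dropout. Part A plans 600 against 248 at 70% v 50% (SAP Table 2).

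**Working it through.** **Inputs from the documents.** Two-sided alpha 0.05 (SAP 10.1), rates 40% and 70%, 120 patients at 1:1, so 60 per arm (SAP 4.2, 4.3).

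**Assumed, because the documents give no figure.** The strength of the relation between Week 16 improvement and Week 44 PASI 90, and the stratum sizes (30% above 100 kg, 20% with prior TNF exposure).

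**1. The plan's own figure.** n per arm = [z₀.₉₇₅√(2p̄(1−p̄)) + z₀.₉₀√(p₁(1−p₁)+p₂(1−p₂))]² / (p₁−p₂)², with p̄ = 0.55.
- (1.960 × 0.7036 + 1.282 × 0.6708)² / 0.30² = 55.7, so 56. This matches Table 1.
- Power at 60 per arm: Φ[(0.30√60 − 1.379)/0.6708] = Φ(1.41) = 92.1%. The stated power above 90% is confirmed.

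**2. Size of chance imbalance.** Split the 50 to <90 range into halves of equal size. The between-arm difference in the share of patients in the upper half has SD √(2 × 0.25/60) = 9.1 points. The chance of an imbalance of 10 points or more is about 27%, of 15 or more about 11%, and of 20 or more about 3%. If Week 44 response differs by 40 points between halves, a 10-point imbalance moves the estimate by 0.10 × 40 = 4 points, against a planned effect of 30.

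**3. Closed-form gain.** The variance term without adjustment is 0.7×0.3 + 0.4×0.6 = 0.45. With a response gap g between halves in both arms it becomes 0.45 − g²/2. Power uses the unpooled formula Φ(0.30/√(v/60) − 1.96).

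| Gap g | Variance term v | SE ratio | Power, 60 per arm |
|---|---|---|---|
| 0 | 0.450 | 1.00 | 93.4% |
| 20 points | 0.430 | 0.98 | 94.3% |
| 40 points | 0.370 | 0.91 | 96.9% |
| 50 points | 0.325 | 0.85 | 98.3% |

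The lower rows are steep assumptions and are best read as a ceiling.

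**4. Simulation of the adjusted test.** Week 44 response is logit-linear in Week 16 improvement, which is uniform over 50-90%, with arm averages calibrated to exactly 40% and 70% and 3,000 runs per cell. The planned test is compared with logistic regression standardised to a marginal risk difference. The ranges below set the strength of the relation before calibration. Left uncalibrated, the strong ranges average 37.9% v 70.8%, a 32.9-point effect, which would overstate power.

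| Relation | Rates at ends of range, adalimumab / risankizumab | Variance | Power change |
|---|---|---|---|
| Weak | 30-50% / 63-77% | about 0% | about −1 point |
| Moderate | 20-62% / 57-82% | about −2% | about 0 |
| Strong | 12-70% / 48-88% | −6 to −9% | +1 to +2 points |

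- In one calibrated run of the strong case at 120 patients, power went from 93.3% to 94.6%.
- Type I error was 5.1-6.3% adjusted and 5.6-6.5% planned. Part of the power loss in the weak case is therefore better control of size.
- A rate near 6% or 93% from 3,000 runs has a standard error of √(0.06×0.94/3000) = 0.4 or √(0.93×0.07/3000) = 0.5 point, so differences below a point should not be read closely.
- The planned estimate correlates with the between-arm difference in Week 16 improvement at about 0.20 (moderate) and 0.32 (strong), on the ranges before calibration. For the adjusted estimate the correlation is about 0.
- Simulated bias of the planned estimator was 0.003 or less.

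**5. Why not a further stratum.** Adding the Week 16 half to the Mantel-Haenszel test makes eight strata of about 120/8 = 15 patients on average. Simulated type I error rose to 7.2-7.6%, against 5.8-6.5% for the planned test in the same runs.

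**The case against.** The strongest reply is that nothing here is broken. Part B is analysed on the factors that stratify its own re-randomisation, which is standard practice. Randomisation makes the estimator unbiased, and its standard error already allows for chance imbalance. Selecting patients on a variable does not oblige the test to use it. All of this stands. A reader might infer from the omission that the test is biased, invalid or short of power; the figures above do not support any of these. Nor do the documents support arms smaller than planned: they give 60 per arm.

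The gain is also conditional. No document figure links Week 16 improvement on adalimumab to Week 44 PASI 90, least of all in patients switched to another drug. Non-responder imputation might dilute the relation further. With an assumed 10% of patients set to failure regardless of Week 16 response, the variance gain was 1-3% (moderate) and 6-9% (strong). This stands as a limit on size, but it leaves a gain in the strong case.

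The last objection is that the change goes beyond SAP wording, because Protocol 7.3.2 fixes this analysis. That is right, and the fix has to cover it. The mention of logistic regression in Protocol 7.5 is only partial support: there it is a sensitivity analysis, and SAP 10.1.4 keeps it only as a fallback if multiple imputation cannot be used.

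**Conclusion.** The point holds as an optional improvement in efficiency and robustness, of low severity. The Part B test and its re-randomisation leave out a measurement that is available for every re-randomised patient and plausibly prognostic. The planned test is nonetheless unbiased and meets its stated power.

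The benefit ranges from nothing to a variance reduction of 6-9% and 1 to 2 points of power. The possible loss is about 1 point of power if Week 16 response is only weakly prognostic. What adjustment reliably adds is an estimate that does not move with chance imbalance in Week 16 response. These sizes rest on the assumed prognostic relations and stratum shares, and on the planned 40% v 70% at 60 per arm.

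**What to change.** Before unblinding:

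- In SAP 10.2, make the Part B analysis of PASI 90 at Week 44 a covariate-adjusted risk difference. Fit a logistic regression on treatment, weight stratum, prior TNF exposure and continuous Week 16 percent PASI improvement, then standardise to a marginal risk difference with a robust standard error.
- Keep the planned stratified Mantel-Haenszel risk difference as a sensitivity analysis.
- Make the matching change to Protocol 7.3.2, which ties this endpoint to the Part A method, and record it in SAP 14.1.
- State which Week 16 value is used (IRT entry or analysis database), what happens if the model does not converge, and whether PASI 100 at Week 44, which follows the same methods under SAP 10.3.1.2, takes the same adjustment.

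The cost is a short program and a documented change to a protocol-specified confirmatory analysis. The statistical price is reliance on a working model, with no gain or up to about 1 point less power if the relation is weak.

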10.3 Secondary Efficacy Analyses

10.3.1 Ranked Secondary Efficacy Analyses

10.3.1.1 Ranked Secondary Efficacy Analysis in Part A

The ranked secondary endpoints in Part A are as follows:

1. Achievement of $\geq 75\%$ reduction from baseline PASI score (PASI 75) at Week 16
2. Achievement of 100% reduction from baseline PASI score (PASI 100) at Week 16

Ranked secondary endpoints above will be analyzed in the ITT_A Population. The same methods as discussed for the primary analyses will be used.

The following null hypotheses will be tested in a hierarchical order using two-sided tests with a type I error of 0.05 only if the null hypothesis for the co-primary endpoints has been rejected:

1. Risankizumab is not different from adalimumab with respect to PASI 75 response at Week 16
2. Risankizumab is not different from adalimumab with respect to PASI 100 response at Week 16

10.3.1.2 Ranked Secondary Efficacy Analysis in Part B

The ranked secondary endpoint for Part B is the achievement of 100% reduction from baseline PASI score (PASI 100) at Week 44.

This ranked secondary endpoint will be analyzed for the ITT_B_RR Population. The same methods as discussed for the primary analyses will be used.

The null hypotheses below will be tested in a hierarchical order using two-sided tests with a type I error of 0.05 only if the null hypothesis for the primary endpoint in Part B has been rejected:

1. Continuation of risankizumab is not different from switching to risankizumab with respect to PASI 100 response at Week 44.

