7.2 NULL AND ALTERNATIVE HYPOTHESES

The primary hypotheses are that BI 655066 is different than adalimumab in achieving $\geq 90\%$ reduction from baseline in the Psoriasis Area and Severity Index score (PASI 90) and sPGA score of clear(0) or almost clear(1) at Week 16 in participants with moderate to severe chronic plaque psoriasis. For the primary analyses, this study has 2 treatment arms (BI 655066 and adalimumab [refer to [Figure 3.1: 1](#)]).

- Arm 1 – Patients randomised at Visit 2 to receive 150mg BI 655066 at Randomisation (Visit 2), Week 4 and then q12 weeks
- Arm 2 – Patients randomised at Visit 2 to receive 80mg adalimumab at Randomisation (Visit 2) and then 40mg adalimumab at Week 1 and then every other week

For the second part of the trial, patients randomised to receive adalimumab at Visit 2 and achieve a PASI 50 response but not PASI 90 at Week 16 will be re-randomised to one of the following treatment arms:

Arm A – Patients re-randomised to receive BI 655066 during the remaining treatment period of the trial

Arm B – Patients re-randomised to continue to receive adalimumab during the remaining treatment period of the trial

The following null hypotheses will be tested in a hierarchical order using two-sided tests with a type I error of 0.05. The co-primary endpoints need to be significant simultaneously, therefore no alpha adjustment is necessary.

1. BI 655066 arm (Arm 1) is not different from adalimumab (Arm 2) with respect to PASI 90 or sPGA score of clear or almost clear (0 or 1) response at Week 16
2. BI 655066 arm (Arm 1) is not different from adalimumab (Arm 2) with respect to PASI 75 response at Week 16
3. BI 655066 arm (Arm 1) is not different from adalimumab (Arm 2) with respect to PASI 100 response at Week 16

For the re-randomised patients, the following null hypothesis test will be performed with a type I error of 0.05.

- BI 655066 arm (Arm A) is not different from adalimumab (Arm B) with respect to PASI 90 response at Week 44 for patients who are re-randomized at Week 16.

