5.0 Analysis Populations

5.1 Definition for Analysis Populations

Efficacy Population:

Intent to Treat (ITT) Populations: The ITT Population in each period will be used for efficacy analyses.

- The ITT Population in Part A (ITT_A) is defined as all subjects who are randomized at Baseline.
- The ITT Population in Part B who are re-randomized (ITT_B_RR) is defined as all subjects who start with adalimumab at Baseline and are re-randomized at Week 16.
- The ITT Population for PASI 90 responders at the entry of Part B (ITT_B_R) is defined as all subjects who start with adalimumab at Baseline and achieve PASI 90 at Week 16 and receive at least one dose of active adalimumab on or after Week 16.
- The ITT Population for PASI 50 non-responders at the entry of Part B (ITT_B_NR) is defined as all subjects who start with adalimumab at Baseline and fail to achieve PASI 50 at Week 16 and receive at least one dose of active risankizumab on or after Week 16.
- The ITT Population in Part B continuously receiving risankizumab (ITT_B_RZB) is defined as all subjects who start with risankizumab at Baseline and receive at least one dose of active risankizumab on or after Week 16.

The ITT Population will be analyzed by the treatment group as randomized and as re-randomized where applicable.

Per-Protocol (PP) Population: To evaluate the impact of protocol deviations on the primary and ranked secondary endpoints, additional analyses will be performed on the Per-protocol Populations. The Per-protocol Population will include those who were most compliant with the protocol in ways that could impact the primary and ranked secondary

endpoints. Final results and the criteria for exclusion of subjects will be determined via classification prior to database lock for data pertaining to the DB period. The PP population at Part A (PP_A) is defined as all ITT_A subjects meeting all the following criteria:

- Subjects must receive at least 75% of planned risankizumab injections, as well as at least 75% of planned adalimumab injections, including dummy placebo injections, per randomized, in Part A.
- Subjects must have either a PASI or sPGA assessment post-baseline in Part A.
- Inclusion Criterion 4: Subjects must have stable moderate to severe chronic plaque psoriasis baseline:
 - Have an BSA $\geq 10\%$ and
 - Have a PASI ≥ 12 and
 - Have an sPGA ≥ 3 .

Primary and ranked secondary efficacy endpoints at Week 16 will be analyzed on the PP_A Population.

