The PP Population at Part B for re-randomized subjects (PP_B_RR) is defined as all subjects from the ITT_B_RR Population who meet all the following criteria:

- Subjects must receive at least 75% of planned risankizumab injections, as well as at least 75% of planned adalimumab injections, including dummy placebo injections, per re-randomized, in Part B.
- Subjects must have at least one PASI assessment post re-randomization in Part B.
- Subjects must have a response of PASI 50 – < 90 at re-randomization.

The primary and ranked secondary efficacy endpoint at Part B at Week 44 will be analyzed on the PP_B_RR Population.

PP Populations will be analyzed by the treatment group as randomized (or re-randomized).

Safety Populations (Safety):

The Safety Populations will be used for safety analyses in different study parts.

Each ITT Population will have a corresponding safety population (Safety) defined which require subjects to have at least one dose of active study drug during the analysis period.

Complete safety tables will be provided for the Safety_A Population and the Safety_B_RR population. AE overview tables will be provided for other safety populations.

The Safety Population will be analyzed based on the actual treatment received at the randomization visit (Safety_A) and at the re-randomization visit (Safety_B_RR).

In addition, an All Risankizumab Treated Population (ALL_RZB) is defined as all subjects who receive at least one dose of risankizumab 150 mg in the study. The ALL_RZB Population will be used for safety analyses. Complete safety tables will be provided in the ALL_RZB Population.

Notations for Treatment Groups:

Part A:

- ADA: Subjects randomized to adalimumab
- RZB: Subjects randomized to risankizumab 150 mg

Part B:

- RZB/RZB: Subjects randomized to risankizumab and continue with risankizumab
- ADA/ADA: Subjects randomized to adalimumab and stay with adalimumab at Week 16
- ADA/RZB: Subjects randomized to adalimumab and switched to risankizumab at Week 16

ALL_RZB:

- RZB: Subjects who received at least one dose of risankizumab 150 mg

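### The ranked Part B hypothesis on PASI 100 at Week 44 names a comparator, continued risankizumab, that has no members in its own analysis population

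*SAP*

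**What the plan says.** SAP 10.3.1.2 makes PASI 100 at Week 44 the only ranked secondary endpoint in Part B. It fixes the population: "This ranked secondary endpoint will be analyzed for the ITT_B_RR Population". It takes its methods from the primary analysis and sets the error rate and gate, with "two-sided tests with a type I error of 0.05 only if the null hypothesis for the primary endpoint in Part B" has been rejected. It then lists a single null hypothesis: "Continuation of risankizumab is not different from switching to risankizumab with respect to PASI 100 response at Week 44".

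The groups are defined elsewhere in the SAP:

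- Section 5.1, on ITT_B_RR: it "is defined as all subjects who start with adalimumab at Baseline and are re-randomized at Week 16".
- Section 4.2, on the two arms: these patients are "re-randomized at a 1:1 ratio to risankizumab or adalimumab".
- Section 5.1, on continued risankizumab: "RZB/RZB: Subjects randomized to risankizumab and continue with risankizumab".
- Section 5.1, on where those patients are analysed: the population "continuously receiving risankizumab (ITT_B_RZB) is defined as all subjects who start with risankizumab at Baseline".

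Protocol 7.2 gives the Part B null for PASI 90 as "BI 655066 arm (Arm A) is not different from adalimumab (Arm B) with respect to PASI 90 response at Week 44". It has no null for PASI 100 at Week 44. SAP 14.1 lists that endpoint among the SAP's own additions, for the re-randomised patients, without naming the comparison.

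**The concern.** The hypothesis and its population exclude each other. One side of the stated contrast, continued risankizumab, requires a patient to have started on risankizumab. Membership of ITT_B_RR requires a patient to have started on adalimumab. No patient can do both.

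This is a confirmatory test that carries alpha. It is also the only formal null that the SAP writes out for Part B, because section 10.2 names the PASI 90 endpoint and population but no null. Read literally, the test either cannot be computed or needs a group from outside the re-randomisation. In neither case does it answer the Part B question of whether partial responders to adalimumab do better by switching than by staying. If the wording is put right only after unblinding, the sponsor is open to the objection that a ranked comparison was altered post hoc.

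**Working it through.** **1. Can the two groups overlap?**

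| Group | Started on | Re-randomised at Week 16? | In ITT_B_RR? |
|---|---|---|---|
| ADA/ADA, re-randomised | adalimumab | yes | yes |
| ADA/RZB, re-randomised | adalimumab | yes | yes |
| RZB/RZB | risankizumab | no | no (ITT_B_RZB) |

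The null compares RZB/RZB with ADA/RZB. Only ADA/RZB is in ITT_B_RR.

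**2. The plan's own Part B figures.** SAP 4.3 assumes 300 adalimumab patients, with PASI 50 in 85% and PASI 90 in 45% at Week 16. The re-randomised pool is 300 × (0.85 − 0.45) = 120, or 60 per arm.

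For 70% versus 40%, two-sided 0.05 and 90% power, the pooled-variance formula is

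n = [1.960 × √(2 × 0.55 × 0.45) + 1.282 × √(0.70 × 0.30 + 0.40 × 0.60)]² / 0.30² = 55.7, so 56 per arm.

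This matches the 56:56 in SAP Table 1. The other rows reproduce to within one patient per arm (computed 82, 81, 54, 52; stated 82, 80, 54, 51). Power at 60 per arm is 92.0%, or 93.4% with unpooled variance, which agrees with the stated figure of over 90%. The sizing fits ADA/RZB against ADA/ADA and is not in question.

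**3. The null as written, in the SAP 10.1.1 formula.** Let n be the continued-risankizumab arm and m the switching arm in stratum i. Every nᵢ is 0.

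- Response rate xᵢ/nᵢ = 0/0, undefined.
- Weight wᵢ = nᵢmᵢ/(nᵢ + mᵢ) = 0 in every stratum, so Σwᵢ = 0.
- The estimate and its variance both divide by Σwᵢ or its square, so neither exists.

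The rule that adds 0.1 to all cells of a stratum with a zero cell does not help. It would give the empty arm 0.1 responders and 0.1 non-responders, a response rate of 0.1/0.2 = 50% whatever the data. That number would come from an arm with no patients.

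**4. Bringing in ITT_B_RZB.** This would set up to about 300 patients, unselected for response, against about 60 switchers selected for a Week 16 response of at least PASI 50 but below PASI 90. The 300 is an upper bound, because ITT_B_RZB requires an active dose on or after Week 16. By the dosing schedule (Protocol Table 4.1.4: 2), the last active risankizumab dose falls 44 − 28 = 16 weeks before Week 44 in continuers and 44 − 32 = 12 weeks before it in switchers. The comparison would be non-randomised and would contradict the population sentence in the same section.

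**5. The contrast the design supports.** ADA/RZB against ADA/ADA in ITT_B_RR can be run with about 60 per arm. The documents give no PASI 100 rates for Week 44, so the power figures below rest on assumed rates only.

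| Adalimumab | Risankizumab | Power, 60 per arm |
|---|---|---|
| 5% | 30% | 96% |
| 10% | 30% | 79% |
| 10% | 40% | 97% |
| 15% | 35% | 72% |
| 20% | 40% | 67% |

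**The case against.** The strongest reply is that this is a one-word slip, risankizumab written for adalimumab, and that the rest of the section shows what is meant. The endpoint, population, method, alpha level and gate are all fixed. ITT_B_RR has exactly two arms, so only one treatment comparison exists within it. SAP 10.1 confines efficacy analysis to ITT_A and ITT_B_RR and has the other populations summarised only, so a comparison with ITT_B_RZB is unlikely in practice. Protocol 7.2 already gives the right pair of arms for PASI 90. Nothing is gated behind this test, and the protocol treats PASI 100 at Week 44 only as a further endpoint, to be described.

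Most of this stands. The intended contrast is hardly in doubt, the figures in step 4 apply only to a literal cross-population test, and the damage is confined to one claim. But a likely explanation for an error does not correct it. The sentence is operative text, it is the only statement of the hypothesis, and no other section gives the PASI 100 null correctly. A confirmatory claim should not depend on readers agreeing to replace the comparator.

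**Conclusion.** The point holds. The comparator named in the only ranked secondary hypothesis of Part B has 0 of about 120 planned members in the stated population, so the test cannot be run as written. This follows from the definitions alone and needs no assumption about response rates. The planned pool of 120 does rest on the Week 16 rates in SAP 4.3.

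The fault lies in the wording of the hypothesis; the endpoint, population and method are usable. The co-primary and ranked tests in Part A, the Part B PASI 90 test and the sample size are untouched. It should nevertheless be corrected before unblinding, because the sentence carries alpha and the protocol offers no PASI 100 hypothesis to replace it.

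**What to change.** Replace the null in SAP 10.3.1.2 with:

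> In re-randomised subjects (ITT_B_RR), switching to risankizumab (ADA/RZB) is not different from continuation of adalimumab (ADA/ADA) with respect to PASI 100 response at Week 44.

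Name the same comparison where SAP 14.1 records the added endpoint. It would also help to write out the matching PASI 90 null in SAP 10.2, which at present states none for Part B.

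The required change is one sentence. It alters no data collection, population, method or sample size. SAP 3.0 has the plan signed off before database lock, so the correction belongs there and should be dated so that it demonstrably precedes unblinding.
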